Empagliflozin is usually a second- or third-line treatment for T2D; thus, it is expected that few patients with T2D initiating empagliflozin will be treatment naïve. For the majority of patients, empagliflozin will be added to an existing treatment (e.g., added to metformin), or patients will be switched to empagliflozin (e.g., from metformin plus an oral glucose lowering medication other than the study drugs to metformin plus empagliflozin) due to disease progression, treatment failure, or side effects that may be related to study outcome. Analyses will account for treatment complexity (monotherapy, dual combination therapy, or triple combination therapy) to achieve a fair comparison between groups [[R13-1120](#), [R14-4378](#)] and concomitant use of metformin (whether a fixed-dose or free combination). Despite the selection of comparators with similar utilization patterns to empagliflozin, the cohorts created with incident users of DPP-4 inhibitor drug group may have inherent channelling bias wherein the treatment assignment is influenced by a range of factors such as disease progression, comorbidity, treatment history, age, and sex. Additionally, some of these variables lead to increased or decreased risk of cancer. To minimize channelling bias, individuals are matched with similar treatment and clinical history at index date by deriving

propensity scores (PS) conditional on factors affecting the treatment and outcome [[R13-1120](#), [R14-4378](#)]. Propensity-score-matched cohorts will be derived from the study base by matching patients who initiate empagliflozin with patients who initiate DPP-4 inhibitors at index date with the highest possible matching ratio (1:1, 1:2, or 1:3 using Greedy matching methods). Depending on sample size, combination exposures with metformin will be accounted for through separate PS, stratification, or adjustment. Additional analyses will explore the presence of detection/diagnostic bias as screening for urinary tract signs or symptoms may be more frequently among empagliflozin users. The potential for diagnostic bias will be evaluated and addressed through consideration of the frequency of urine dipstick testing (as captured through albuminuria tests) and stage of cancer at the time of diagnosis (as more early-stage cancers in one group would be suggestive of diagnostic bias).

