8.3.1 Exposures

Empagliflozin (current ATC code A10BK03, previous ATC code A10BX12) is the exposure of interest, free or fixed-dose combination with metformin (ATC code: A10BD20).

The DPP-4 inhibitor comparator exposure group will consist of the following drugs, free or fixed-dose combination with metformin (See [Section 8.1](#) and [Annex 4](#)).

- Alogliptin
- Linagliptin
- Saxagliptin
- Sitagliptin
- Vildagliptin

If additional DPP-4 inhibitors are introduced in any of the study countries during the study period, they will also be considered to be members of the corresponding comparator group. Note that use of any of these index drugs prior to index date is an exclusion criterion.

Information on whether patients received prior oral glucose lowering therapy or if they were “added on” or “switched to” empagliflozin, or a DPP-4 inhibitor at the time of inclusion in the study will be collected. Patients will be classified according to their treatment complexity as receiving monotherapy, dual combination therapy, or triple combination therapy and according to use of metformin combination therapy (fixed-dose or free combination). (See Section 8.1)

The primary definition of exposure, i.e., as-treated analysis (AT), is defined as an ongoing exposure (free or fixed-dose combination with drugs other than DPP-4 inhibitors and SGLT-2 inhibitors) to one of the following two index drugs or drug groups: empagliflozin or DPP-4 inhibitors ([Table 3](#), Annex 4). Exposure is defined as use of these drugs during the study period starting from 6 months after the index date (see [Sections 8.2.3](#) and [8.3.5](#))

As a typical prescription length is one month in the UK and three months in Sweden and Finland, multiple prescriptions are required for a patient to have continuous ongoing treatment at 6 months after index date. Therefore, patients with only one prescription are unlikely to contribute to the AT analysis.

Secondary definitions of exposure include cumulative dosage of empagliflozin use, daily dosage of empagliflozin prescribed per use (10mg vs 25mg), and time since first dose of empagliflozin ([Table 3](#), Annex 4).

Sensitivity analyses of exposure include intention-to-treat (ITT) analyses.

Table 3

Exposure definitions for primary and secondary analyses

Exposure definition	Description	Time-dependent or Fixed at index date

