Current exposure to study treatment (as-treated analysis)	Indicator of current use of empagliflozin, or a DPP-4 inhibitor, either alone or as a combination.	Time-dependent
Exposure to Empagliflozin (Intention-to-treat)	Drug purchased/prescribed at index date, which is one of empagliflozin, or a DPP-4 inhibitor.	Fixed at index date
Cumulative dosage of empagliflozin use	Time-dependent cumulative sum of drug consumption based on the daily defined dosage of empagliflozin since entry into the study cohort.	Time-dependent
Daily dosage of empagliflozin per use	The dosage of empagliflozin prescribed per daily use (10mg vs 25mg).	Time-dependent
Time since first dose of empagliflozin	Time-dependent cumulative sum of duration since the first use of (exposure to) empagliflozin.	Time-dependent
Treatment complexity	Monotherapy, dual combination therapy, or triple combination therapy (based on predefined groups).	Fixed at index date
Switch	Switch from the drug purchased/prescribed on index date to any other drug in the primary exposure.	Time-dependent
Concomitant use of insulin	Was empagliflozin an add-on to insulin (yes/no).	Fixed at index date
Concomitant use of metformin	Was empagliflozin an add-on to metformin (yes/no).	Fixed at index date
Concomitant use of metformin	Concomitant use of metformin either as fixed-dose combination or free combination.	Time-dependent
Ever used other oral glucose lowering medication	Use of other oral glucose lowering drugs based on predefined drug groups in the past.	Time-dependent
Ever used metformin	Was metformin ever used – taking value 'yes' as soon as one prescription with metformin is purchased.	Time-dependent

Exposure definition	Description	Time-dependent or Fixed at index date
Ever used sulphonylureas	Was sulphonylureas ever used – taking value ‘yes’ as soon as one prescription with sulphonylureas is purchased.	Time-dependent
Ever used thiazolidinediones	Was thiazolidinediones ever used – taking value ‘yes’ as soon as one prescription with thiazolidinediones is purchased.	Time-dependent
Ever used GLP-1	Was GLP-1 ever used – taking value ‘yes’ as soon as one prescription with GLP-1 is purchased.	Time-dependent
Ever used insulin	Was insulin ever used – taking value ‘yes’ as soon as one prescription with insulin is purchased.	Time-dependent

GLP=glucagon-like peptide

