8.3.3 Covariates

Variables potentially associated with urinary tract cancers, such as socio-demographic variables including age, sex, socioeconomic status, body mass index, smoking and alcohol consumption, laboratory measurements, concomitant medications, comorbidities, and duration of look-back period (see [Section 6.1](#)), will be identified for study participants as recorded prior to the index date (see [Annex 6](#) for list of covariates to be included in the study). With the exception of exposure to toxic chemicals such as arsenic, known risk factors for urinary tract cancers are captured in CPRD and the national registers from Sweden and Finland.

Study participants will also be classified by indicator variables on the calendar time of cohort entry (by quarter) whether the index treatment (empagliflozin, or DPP-4 inhibitor) was added to existing medication (adding on), or if the index treatment was initiated as a replacement for another antihyperglycemic medication (switching to empagliflozin, or DPP 4 inhibitor), and whether this treatment was received as monotherapy or as dual or triple combination therapy. A variable indicating whether or not patients were receiving insulin at the index date will also be created.

The confounding due to covariates in this section are to be accounted for at minimum by design or analysis when estimating the risk of urinary tract cancers with the defined

The examples of covariates in Table 4 describe the comorbidities, treatment history, and socio-demographic variables that will be considered for inclusion. These variables along with times of occurrence/diagnosis of comorbidities, times of prescription/dispensing of drugs and times of recording of the socio-demographic variables in combination with the exposure and outcome variables define the minimal required dataset.

Table 4

Baseline covariates to be considered for inclusion alternatively or simultaneously in primary, secondary, and further analyses

Covariate	Exact matching	PS matching	Stratification	
Database variable (for CPRD only) ¹				
Patient database (Aurum vs GOLD)	Yes	Yes		
Socio-demographic variables				
Age	Yes	Yes	Yes	
Sex	Yes	Yes	Yes	
Socioeconomic status (if available)		Yes		
Calendar year of index date		Yes		
Duration of look-back period		Yes		
Insulin concomitant (or cumulative duration of) use		Yes	Yes	
Other oral antihyperglycemic medication use		Yes		
Comorbidities				

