ANNEX 4. CODES TO IDENTIFY EXPOSURE VARIABLES

No.	Variable	ATC codes ³	Time-dependent (T) / fixed at cohort entry (F)	How the effect of variable is accounted for ¹
1	AT / ITT: Empagliflozin	Empagliflozin A10BK03 (current), A10BX12 (previous)	T / F	E
2	AT / ITT: DPP-4 inhibitor	DPP-4 inhibitors ATC beginning with A10BH Fixed-dose combinations Will be identified from ATC class A10BD	T / F	E
3	AT / ITT, FDCM ² : empagliflozin		T / F	E
4	AT / ITT, FDCM ² : DPP-4 inhibitor		T / F	E
5	Empagliflozin current use		T	E
6	Empagliflozin: cumulative duration of exposure		T	E
7	Empagliflozin: cumulative dosage of exposure		T	E
8	Empagliflozin: time since last dose		T	E
Other OAD treatments				
9	Metformin	ATC beginning with A10BA	T	PS / A / VS, RS, TV, SG
10	Sulphonylureas	ATC beginning with A10BB	T	PS / A / VS, RS, TV

No.	Variable	ATC codes ³	Time-dependent (T) / fixed at cohort entry (F)	How the effect of variable is accounted for ¹
11	Insulin	ATC beginning with A10A	T	PS / A / VS, RS, TV
12	Thiazolidinediones	ATC beginning with A10BG	T	PS / A / VS, RS, TV
13	Alpha glucosidase inhibitors	ATC beginning with A10BF	T	PS / A / VS, RS, TV
14	GLP-1 agonists	Will be identified from ATC classes A10BJ and A10BX	T	PS / A / VS, RS, TV
15	Other blood glucose lowering drugs, excluding insulins	ATC beginning with A10BX that is not included elsewhere		
16	Treatment complexity (mono, dual and triple combination therapy)		T	PS / A / VS, RS, TV
17	Switch or add-on		T	PS / A / VS, RS, TV
Exclusion / Censoring				
18	DPP-4 (Linagliptin) and Empagliflozin	A10BD19	T	Censoring / Exclusion
19	Discontinuation of primary exposure		T	Censoring
20	Switch to other SGLT-2 inhibitor use	A10BK02, A10BX11, A10BK01, A10BX09, A10BK04, A10BD16, A10BD15, A10BD23	T	Censoring / Exclusion

No.	Variable	ATC codes ³	Time-dependent (T) / fixed at cohort entry (F)	How the effect of variable is accounted for ¹
21	Use of fixed-dose combinations of SGLT-2 inhibitors with DPP-4 inhibitors	Identified from ATC class A10BD	T	Censoring / Exclusion

¹ E – Exposure, A – adjusted in the Cox model, VS – potential confounder and will be adjusted for using variable selection, PS – one of the PS matching variable at baseline, TV – time-varying confounder and adjusted for in MSM, RS – defines the risk set in NCC, SG – used as a subgroup in stratified analyses, / - and/or

2 FDCM – Fixed-dose combination with metformin

3 New drugs will be included in the variable definitions if they become available during the study period.

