5. VARIABLES

5.1. EXPOSURES

5.1.1. STUDY MEDICATIONS

Main Cohort:

In each country, after identifying the study cohort, patients will be grouped in two exposure groups:

- New users of empagliflozin: Patients prescribed empagliflozin at index date.
- New users of DPP-4 inhibitors: Patients prescribed any DPP-4 inhibitor at index date.

Sub-cohort of users of empagliflozin in combination with metformin

Patients using metformin in free or fixed dose combination will be identified in the main study cohort and grouped in two exposure groups for a separate analysis:

- Patients prescribed empagliflozin in free or fixed dose combination with metformin at index date.
- Patients prescribed any DPP-4 inhibitor in free or fixed dose combination with metformin at index date.

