Ever exposed to other glucose lowering medication	Variable indicating any use of oral glucose lowering drugs other than the study drugs using data from 180 days prior to index date onwards.	Time-dependent Categorical: Yes No	UK: CPRD Sweden: SPDR Finland: FPR
	ATC codes for other glucose lowering drugs in Annex II.		
Updating from 180 days prior to index date onwards.			
Treatment complexity at index	Treatment complexity at index date is categorized by the number of drug classes in concomitant use including study drugs, using data from 180 days prior to index date onwards.	Time-fixed Categorical: Monotherapy Dual combination therapy Triple combination therapy or higher	UK: CPRD Sweden: SPDR Finland: FPR
	Evaluated at index using data from 180 days prior to index date onwards.		

Table 15 Other non-diabetic concomitant medication use variables

Variable	Definition	Details	Data source
Antihypertensive s/diuretics exposure at index date	Exposure status at index date of any antihypertensives/diuretics (including combinations) based on purchased amounts and daily defined dose using data within 180-day period prior to index date. ATC codes for antihypertensives/diuretics in Annex II. Evaluated at index date using data within 180-day period prior to index date.	Time-fixed Categorical: Yes No	UK: CPRD Sweden: SPDR Finland: FPR
Non-steroidal anti-inflammatory drugs (NSAIDs) exposure at index date	Exposure status at index date of any NSAID (including combinations) based on purchased amounts and daily defined dose using data within 180-day period prior to index date. ATC codes for NSAID in Annex II. Evaluated at index date using data within 180-day period prior to index date.	Time-fixed Categorical: Yes No	UK: CPRD Sweden: SPDR Finland: FPR
Oral steroids exposure at index date	Exposure status at index date of any oral steroid (including combinations) based on purchased amounts and daily defined dose using data within 180-day period prior to index date. ATC codes for oral steroids in Annex II. Evaluated at index date using data within 180-day period prior to index date.	Time-fixed Categorical: Yes No	UK: CPRD Sweden: SPDR Finland: FPR

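### The SAP has no add-on versus switch indicator, which the protocol calls for, and its treatment-complexity variable cannot stand in for it

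*SAP*

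**What the plan says.** **Protocol.** Section 8.3.1 asks for add-on or switch status to be recorded for each patient: "if they were “added on” or “switched to” empagliflozin, or a DPP-4 inhibitor at the time of inclusion in the study will be collected". Section 8.3.3 classifies patients by whether the index treatment "was added to existing medication (adding on), or if the index treatment was initiated as a replacement" (the drug replaced being some other glucose-lowering agent), and then asks that confounding from the covariates of that section be dealt with, as a minimum, in the design or the analysis. Annex 4 row 17, "Switch or add-on", carries the roles PS, adjustment or variable selection, nested case-control risk set and time-varying confounder. Its footnote reads the slash between roles as and/or. Section 8.1 says that patients add or change to empagliflozin "due to disease progression, treatment failure, or side effects that may be related to study outcome".

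**SAP.** Sections 6.5.1 and 6.6.2 take the PS candidates and the balance covariates from Tables 11 to 15. The base model (6.7.2) adjusts only for PS variables that remain unbalanced. None of these tables has an add-on or switch item. Table 14 has treatment complexity at index, a time-fixed variable "categorized by the number of drug classes in concomitant use including study drugs, using data from 180 days prior to index date onwards". The metformin sub-cohort (5.1.1) is defined by "Patients prescribed empagliflozin in free or fixed dose combination with metformin at index date", with a parallel line for DPP-4 inhibitors.

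**The concern.** The protocol treats the circumstances in which the index drug was started as a source of channelling and names a covariate for them. If the SAP is programmed as written, that covariate is absent from the PS. An imbalance in it would not appear in the post-matching balance table, and it could not return through the base model, which draws only on PS variables. The adjusted model's list of time-dependent variables does not contain it either.

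Treatment complexity is the only variable that comes close. If it gives the same value to a patient who replaced a drug and a patient who added one, the strata labelled monotherapy, dual and triple therapy mix the two groups, and matching on complexity does not balance them.

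**Working it through.** The documents state no figure for this variable, so the check compares texts, with some counting.

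**1. Tracing the variable.** It is required in Protocol 8.3.1 and 8.3.3 and given a role in Annex 4 row 17. It is not in SAP Tables 11, 12, 13, 14 or 15, nor in the Table 18 balance shell. The SAP change log (section 3) mentions moving some covariates from time-dependent to time-fixed but records no removal of this one. Row 11 of the log is not readable, and the redacted nested case-control and marginal structural model sections could not be checked.

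**2. Can complexity replace it?** Protocol 8.1 gives its own example of a switch: from metformin plus another oral drug to metformin plus empagliflozin. A sulfonylurea is assumed here as the other drug. Class counts, study drug included:

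| Patient | Any class in the window | Supply covers index, replaced drug has supply left | Only classes really continued |
|---|---|---|---|
| Metformin replaced by empagliflozin | 2 | 2 | 1 |
| Empagliflozin added to metformin | 2 | 2 | 2 |
| Metformin + sulfonylurea, sulfonylurea replaced | 3 | 3 | 2 |
| Empagliflozin added to metformin + sulfonylurea | 3 | 3 | 3 |

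The SAP does not say which of the first two columns applies. In both, switch and add-on receive the same count. Under the supply reading the counts fall to 1 and 2 only when the replaced drug had lapsed before the index date.

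**3. Why the definition of concomitant matters.** Protocol 8.3.1 gives typical prescription lengths of one month (UK) and three months (Sweden, Finland); SAP 5.1.6 gives a 30-day grace period. With months taken as 30 days, for a last fill on day −180:

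- UK: supply ends on day −180 + 30 = −150, and with grace on day −120.
- Sweden and Finland: supply ends on day −180 + 90 = −90, and with grace on day −60.

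Such a drug counts if any use in the window qualifies, and does not count under a supply rule. A last UK fill is already lapsed beyond grace at index over 120/180 = 67% of the window; for Sweden and Finland the share is 60/180 = 33%. The choice of reading therefore changes the variable.

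**4. Post-index data.** Taken literally, *onwards* lets a class started after index raise a time-fixed index variable. The protocol abstract takes covariates from codes before the index date unless otherwise specified. SAP 6.5.1 conditions the PS on history up to the index date, and SAP 6.3 relies on information before or at index for exposure and study entry.

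**5. Metformin.** Fixed-dose combinations are unambiguous. For free combination, Table 14 has a current-exposure status based on purchased amounts and daily dose, but 5.1.1, 6.4 and 6.5.2 do not say that this status defines the cohort or the exact match. A patient who replaced metformin but still holds supply would be read as a user.

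**6. Outputs touched.** Table 16 plans 3 outcomes × 3 complexity strata × 3 countries = 27 tables, and the corresponding 3 × 3 = 9 of the 54 stratified meta-analysis figures. The PS underlies both matched cohorts in each country.

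**The case against.** Several points against the concern are sound.

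- The SAP counts classes *in concomitant use*. It does not say that every class seen since day −180 counts. A reader might infer that from the 180-day window, but Table 14 says any use where it means it (the ever-exposed rows), Table 15 pairs a 180-day window with a supply-based status, and section 5.1.4 provides a days' supply method. The defect is that concomitant use is undefined.
- A reader might also infer that the metformin cohort is filled with patients who never took the combination. The supply-based metformin status does not support that; only leftover supply is at issue.
- The sentence in Protocol 8.1 covers adding as well as switching. It does not say that switching predicts cancer, and the text goes on to name treatment complexity and metformin use as what the analyses will account for.
- Protocol 8.7.1.1 points to Annex 6 for PS candidates, and Annex 6 lacks this variable. Annex 4's and/or does not compel PS inclusion, and section 8.3 leaves the final list to the SAP.
- The Table 17 shell shows use prior to index and at index separately for several classes, so replacement would be partly visible.
- The variable is labelled as at index, so a careful programmer might ignore *onwards*.

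The omission remains. Annex 6 also lacks metformin, insulin and treatment complexity, which Annex 4 gives PS and/or adjustment roles, so absence there is not a decision to drop. Deferral to the SAP does not remove the minimum set in 8.3.3. Table 17 describes patients before matching; Table 18 keeps only at-index use, and Table 14 defines no index-date status for sulfonylureas, thiazolidinediones or GLP-1 drugs.

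**Conclusion.** The concern holds in this form. A covariate that the protocol says will be created and accounted for is missing from every readable covariate table in the SAP without a recorded reason, and treatment complexity does not substitute for it under either plausible reading. The *onwards* wording is a separate defect in the same variable.

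The size cannot be stated. The documents give no share of switchers, no imbalance between arms and no outcome rate by switch status. Matching on HbA1c, diabetes duration, eGFR and background drugs may absorb part of any imbalance. A bias could run either way, and no bias figure should be claimed. What can be stated is the reach: the PS and balance check in each country, and 27 stratified tables. The conclusion assumes that the redacted sensitivity sections and the unreadable change-log row do not restore or explain the variable. Even if a sensitivity section uses it, it would still be missing from the readable tables that feed the primary PS.

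**What to change.** 1. Restore the add-on/switch indicator in SAP Table 14, the PS candidate list (6.5.1) and Table 18, derived from dispensing data up to and including the index date. State the inclusion of the index date explicitly, because the protocol abstract otherwise excludes it. If the indicator is to stay out, record the reason in section 3.
2. Define treatment complexity at index as the study drug plus every class whose days' supply (5.1.4), with the 30-day grace, covers the index date. Delete *onwards*.
3. Define free combination with metformin at index by the same rule, for both the exact match and the sub-cohort.
4. Keep any version that uses refills after index as a sensitivity analysis. A 90-day refill window would be too short: a 90-day fill just before index plus 30 days' grace runs to about day 120, which is still inside the 180-day latency period.

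The cost is SAP text and programming on dispensing data already held. The limitation is that data up to the index date cannot identify a drug replaced on that date with supply left, so some switches will be read as add-ons. The sensitivity version would show how much that matters.
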